# Data Safety Monitoring and Reporting Plan:

Analysis: An interim analysis of results shall be performed at midpoint of the study (100 patients randomized). The final analysis will be performed once 100 evaluable patients have been enrolled in the study.

The Primary Investigator or Study Coordinator will monitor the research clinical study in a manner consistent with the applicable health authority regulations and the clinical standards adopted by the investigators.

The scope of the Primary Investigator or designated Study Coordinator's responsibilities include:

- Working with each Investigator and office staff to assure that the protocol, responsibilities and record keeping requirements are understood prior to initiation of the study
- Maintaining close contact with the investigators concerning the progress of the study
- Monitoring the study progress on a regular basis, semi-annually or more frequently
- Handle data entry and/or analysis
- Report Adverse Events in a timely manner

The reporting and monitoring process will be assisted by the following tools:

- A Study Data File for each patient will be created to maintain the information for each patient enrolled in the study. It will include copy of signed/dated Informed Consents and any adverse event reports.
- All submitted clinical data will go through quality assurance review, data entry and statistical analysis.

A Data and Safety Monitor (DSM) will be designated as [name], CNOR, RNFA, CBN who will meet with study coordinator and Principal investigator following enrollment of 100 subjects and will have access to the de-identified data. The role of the DSM will be to:

- Evaluate the collected data for participant safety, study conduct and progress
- Make recommendations concerning continuation, modification, or termination of the trial.

The study may be stopped for one or more of the following reasons:

- Study aims met at the first analysis
- A finding of no significant differences between therapeutic groups
- The DSM determines there are significant safety issues

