#### Sample Size:

Approximately 200 patients (100 patients in each arm) are expected to participate in the study. These patients are those that have fulfilled NIH criteria and met preoperative requirements for bariatric surgery. Surgeries and hospital care will be at Fresno Heart and Surgical Hospital (FHSH). Post-operative visits will be at Advanced Laparoscopic Surgical Associates (ALSA).

Methodology used to determine sample size: Utilizing existing data, an estimate was made as to the magnitude of benefit that could be expected for the parameters of interest. Using these estimates, a power analysis was performed to determine the number of patients that would need to be present in each arm for a statistically significant difference at 95% confidence level. Next the estimate of the benefit was reduced to come with the actual number of patients for the study.

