After discharge, patients will receive a questionnaire to rate daily pain score, daily nausea score, and number of narcotics taken each day. At the first post-operative visit (generally around post-operative day 7), they will be seen by a clinical investigator to review medications, questionnaires, and if any complications relating to surgery or medications administered. Questionnaires and patient journals pertaining to the study will only be limited up until the first post-operative visit.

Patients will be followed as part of standard post-operative bariatric surgery protocol where visits in the office will occur one week post operatively, three weeks post operatively, then routinely every 3-4 months afterwards routinely or more often depending patient routine needs after bariatric surgery. Routinely, patients are then

seen annually in the office as part of their routine health care. There are no additional follow up requirements because patients were involved in the study.

Data will then be analyzed to determine if liposomal bupivacaine has decreased number of total morphine equivalents and has a beneficial effect on surgical care, post-operative nausea, hospital length of stay and readmissions.

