## **Statistical Analysis**:

Descriptive statistics will be performed on all patients and the demographic data will be examined and compared. Poisson Regression, student's t-test, and non-parametric testing will be used for the analysis of continuous variables. Chi-square analysis will be used for categorical data.

This interventional study is designed to test the null hypothesis that the rate of morphine equivalent units utilized by patients who were administered liposomal bupivacaine (Exparel®) during a primary bariatric surgery is greater than or equal to the rate of patients who were administered Marcaine, versus the alternative hypothesis that the rate of morphine equivalent units utilized by liposomal bupivacaine (Exparel®) during patients is lower than that of bupivacaine only patients. Testing of this hypothesis will be performed for the time period of the inpatient stay, as well as for the period of 7-10 postoperative days.

The sample size selected for this study was chosen to allow for a power of 0.90, an alpha of 0.05, and the ability to detect a rate change of as low as 10% or a 11 unit difference in average daily morphine equivalent units utilized. NCSS/PASS was the statistical software package used for the sample size calculations.

A combination of NCSS and RStudio will be used for the statistical analysis of this study.

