# Data Security:

All data will be maintained on a firewall and password protected shared drive maintained by investigators, sub investigators, and clinical staff. Patients assigned to randomized treatment group will have patient identifier label and entered into secure database by study coordinator. Patient label and study assignment will be placed into a secure locked box and collected at end of each operating day. The information will be entered by the study coordinator or study staff and the patient label and randomization cards will be placed in secure CMC vendor approved shredding boxes immediately afterwards. This will be completed daily and by 1-2 assigned study staff who will maintain chain of custody of patient information. Patient questionnaires and dairies will also be collected and stored following HIPAA regulation and locked in secure room.

Data collection, information from patient diaries and questionnaires from ALSA and data collection from CMC electronic health records will be placed on password protected file on Fresno Heart and Surgical hospital server drive with limited rights access. All patient information will be de-identified prior to analysis. The data safety monitoring monitor (DSM) will meet (in person or via conference call) following enrollment of 100 subjects and will have access to only de-identified data.

All data collected during the study that contains any patient identifiers will be destroyed upon completing the publications relevant to this study. Data that is stored electronically will be erased from all electronic storage locations. Any paper records that are collected will be destroyed via shredding using a CMC approved vendor.

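### The final analysis is set at 100 evaluable patients, half the planned 200 and the same count as the interim; evaluable is not defined

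*Combined protocol and SAP*

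**What the plan says.** - **Planned size.** The Sample Size section says: "Approximately 200 patients (100 patients in each arm) are expected to participate in the study".
- **Interim.** The Data Safety Monitoring and Reporting Plan says: "An interim analysis of results shall be performed at midpoint of the study (100 patients randomized").
- **Final.** The next sentence of that section says: "The final analysis will be performed once 100 evaluable patients have been enrolled in the study".
- **Data and Safety Monitor (DSM).** The same section has the DSM meet after 100 subjects are enrolled. Data Security repeats this timing ("following enrollment of 100 subjects and will have access to only de-identified data") without calling it an interim. One of the DSM's tasks is: "Make recommendations concerning continuation, modification, or termination of the trial". One listed reason for stopping is: "Study aims met at the first analysis".
- **Power.** Statistical Analysis says: "The sample size selected for this study was chosen to allow for a power of 0.90, an alpha of 0.05", for a 10% rate change or an 11-unit difference in average daily morphine equivalents. It gives no SD and no patient count.
- **Timing of analysis elsewhere.** The text under Randomization ends its account of follow-up with "Data will then be analyzed to determine if liposomal bupivacaine has decreased number of total morphine equivalents". That places the analysis after follow-up but gives no number.
- **Evaluable.** The word occurs only in the final-analysis sentence. The documents give no definition, analysis population or dropout allowance.

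**The concern.** A trial whose midpoint is 100 randomised patients cannot also have its final analysis at 100 patients in total. The sentence that fixes the final data cut contradicts both the sample size section and the sentence before it.

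Two things are at stake. If the sentence is followed as written, the final analysis uses half the planned sample and adds little to an interim look at which the trial may already be stopped. If it is a slip, the plan still does not say whether the intended total counts randomised or evaluable patients. The two counts can differ: randomisation takes place before induction of anaesthesia, whereas some of the listed intraoperative exclusions, such as an operation longer than 3 hours or conversion to open surgery, can be known only afterwards. An undefined evaluable count also leaves the date of the final cut open to judgement after interim results have been seen.

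**Working it through.** **1. Do the counts agree?** Half of 200 is 100, so the interim trigger fits the Sample Size section. The final trigger of 100 does not; it is too small by a factor of 200 / 100 = 2. The DSM's advice on continuation and the reference to a first analysis also presuppose a later analysis on more patients. This contradiction rests on no assumption.

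**2. Can the planned size be reproduced?** No, because no SD is stated. It can only be back-solved. The inputs from Statistical Analysis are a difference of 11 units, power 0.90 and alpha 0.05; allocation is 1:1 (Randomization). The hypotheses are worded one-sided but the sidedness of alpha is not given, so both are shown. With n = 100 per arm and the normal approximation:

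SD = 11 × √(100/2) / (z_α + z_β)

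- Two-sided: 11 × 7.071 / (1.960 + 1.282) = 24.0
- One-sided: 11 × 7.071 / (1.645 + 1.282) = 26.6

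The exact noncentral t gives 23.9 and 26.5.

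**3. Power at 50 per arm, if 100 per arm gives exactly 0.90.** Halving n divides the noncentrality by √2:

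power = Φ((z_α + z_β)/√2 − z_α)

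- Two-sided: Φ(3.242/1.414 − 1.960) = Φ(0.332) = 0.63 (exact t: 0.626)
- One-sided: Φ(2.926/1.414 − 1.645) = Φ(0.424) = 0.66 (exact t: 0.662)

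The difference detectable with power 0.90 rises to 11 × √2 = 15.6 units.

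**4. If the planned size has slack.** The Sample Size section says the benefit estimate was reduced in arriving at the actual number, so 0.90 may be reached below 100 per arm. Taking 90 or 80 per arm as assumed calibration points (exact t):

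| 0.90 reached at | Power at 50 per arm, two-sided | One-sided |
|---|---|---|
| 100 per arm | 0.626 | 0.662 |
| 90 per arm | 0.672 | 0.702 |
| 80 per arm | 0.723 | 0.746 |

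**5. If variance is purely Poisson.** Equating 11 units with 10% implies means of 110 and 99 (one day per patient assumed).

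n per arm = (z_α + z_β)² × (110 + 99) / 11²

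- Two-sided: 10.507 × 209 / 121 = 18.1, so 19
- One-sided: 8.564 × 209 / 121 = 14.8, so 15

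At 50 per arm power exceeds 0.99 and the loss is negligible. This model would not call for 100 per arm, however. For 100 per arm to give exactly 0.90, the variance would have to be about 100/18.1 = 5.5 (two-sided) to 100/14.8 = 6.8 (one-sided) times the mean.

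**6. Overlap with the interim on the literal reading.** The non-evaluable rates are assumed; the documents give none.

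| Non-evaluable | Evaluable among first 100 randomised | Randomised to reach 100 evaluable | Randomised to reach 200 evaluable |
|---|---|---|---|
| 0% | 100 | 100 | 200 |
| 5% | 95 | 100/0.95 → 106 | 200/0.95 → 211 |
| 20% | 80 | 100/0.80 = 125 | 200/0.80 = 250 |

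Between 80 and 100 of the final 100 patients would already have been in the interim.

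**The case against.** The strongest reply is that this is an evident slip. Every other statement points to about 200 patients, and the sentence may simply lack the words per arm, so it is incomplete rather than wrong. On that reading no power is lost. The power figures also carry limited information: no SD is documented, 0.90 at 100 per arm holds by construction, the 80 and 90 per arm cases are arbitrary, and the range under the literal reading runs from 0.63 to above 0.99.

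Much of this is fair. The slip reading is the more plausible one, and only the factor of 2 is firm. But a final-analysis trigger should not have to be inferred, least of all in a plan that allows stopping at the same count. Calling it a slip does not settle the matter either, because the sentence could be repaired as 100 evaluable per arm or as 200 randomised in total, and these are different numbers of patients.

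A second objection is that moving the count from evaluable to randomised is not purely editorial. That is also fair. If 0.90 needs exactly 100 analysed per arm and 5% to 20% of 200 randomised patients are not analysed (assumed), 95 to 80 per arm remain and power is about 0.89 to 0.83. The fix therefore includes a power check and leaves the evaluable basis open to the sponsor.

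Third, the Randomization text says the study coordinator will track the intraoperative exclusions from the electronic record. This is the nearest the documents come to an evaluability process, but it does not define the term.

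**Conclusion.** The concern holds and must be fixed. The only sentence that gives a count for the final analysis contradicts the Sample Size section and the sentence before it by a factor of 2. That conclusion rests on the text alone.

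The consequence depends on what was meant. If it is a slip, the loss of power is zero and what remains is the unstated counting basis. If it is literal, about 50 per arm are analysed. Power is then about 0.63 to 0.66 if 100 per arm was needed for 0.90 under a t-test, about 0.67 to 0.75 if 80 to 90 per arm sufficed, and above 0.99 under pure Poisson variance. These figures illustrate the range; none can be confirmed without the sponsor's SD.

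**What to change.** Replace the final-analysis sentence in the Data Safety Monitoring and Reporting Plan with wording such as:

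> The final analysis takes place after 200 patients have been randomised (100 per arm) and each has either completed the 7–10 day postoperative period or left the study.

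This drops the undefined word. It also names the later of the two periods in Statistical Analysis, the other being the inpatient stay; the sponsor should confirm that this period is the one meant. Then:

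- **If 200 counts randomised patients**, check from the sponsor's own SD whether 0.90 still holds for the number expected to be analysed, and restate the power in Statistical Analysis only if it does not.
- **If evaluable patients are meant**, say so, define the term, give the count in total or per arm, and state how many will be randomised.
- **If 100 in total is really intended**, restate the Sample Size section, the interim timing and the power from the sponsor's own inputs.

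**Cost.** One sentence and no extra patients if 200 counts randomised patients, plus a power restatement if the check fails. If 200 evaluable are wanted, about 11 more patients would be randomised at 5% non-evaluable and 50 more at 20% (both rates assumed).

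### Stopping at 100 patients for success or for non-significance has no boundary or futility threshold, so alpha 0.05 and power 0.90 are not both assured

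*Combined protocol and SAP*

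**What the plan says.** Under Data Safety Monitoring and Reporting Plan, an interim analysis of results takes place at 100 randomized patients, described as the midpoint. The same section states: "The study may be stopped for one or more of the following reasons". Three reasons are listed:

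- "Study aims met at the first analysis"
- "A finding of no significant differences between therapeutic groups"
- significant safety issues, as determined by the Data and Safety Monitor

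The monitor's task at that point is to "Make recommendations concerning continuation, modification, or termination of the trial". No statistical criterion is attached.

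The section also says "The final analysis will be performed once 100 evaluable patients have been enrolled in the study", whereas the Sample Size section says "Approximately 200 patients (100 patients in each arm) are expected to participate in the study".

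The Statistical Analysis section gives a single alpha of 0.05, not labelled one- or two-sided, and a power of 0.90. Its null hypothesis is directional: the opioid rate under liposomal bupivacaine "is greater than or equal to the rate of patients who were administered Marcaine". It does not mention the interim look.

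**The concern.** Safety is a separate item, so the first two reasons are stops based on outcome. Neither says what result triggers it.

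The two reasons pull in opposite directions. Stopping on a significant interim and otherwise continuing gives the trial two chances to claim success, which raises the false-positive risk. Stopping on a non-significant interim does not raise that risk, but it discards power, because non-significance at half the sample is weak evidence of no effect.

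Nothing written in advance says which use applies. A reader of the final report could not tell which error rates the result carries, and this cannot be credibly repaired once the results at 100 have been seen.

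The unclear final number makes it worse: 100 is both the midpoint and the trigger for the final analysis. That may be a slip for 100 per arm, but no boundary can be set until it is settled.

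**Working it through.** **The plan's own figure.** The 200 patients cannot be reproduced, because no standard deviation is given. With a difference of 11 units, power 0.90 and 100 per arm, the implied SD is 11 / [(z_α + 1.2816) × √(2/100)]. This is 26.6 if alpha is one-sided and 24.0 if two-sided. The error rates below do not need the SD; the power figures take the stated 0.90 at 200 as given.

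**Inputs.** Alpha 0.05 and power 0.90 (Statistical Analysis); about 200 patients (Sample Size); look at 100 (Data Safety Monitoring and Reporting Plan), so information fraction t = 0.5. Assumed: one test, and unadjusted 0.05 at each look.

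**Model.** The interim and final statistics Z1 and Z2 are bivariate normal with correlation √t = 0.7071, and positive values favour liposomal bupivacaine. Under the design effect the mean of Z2 is θ = z_α + 1.2816 and the mean of Z1 is θ√t. Critical values are c = 1.645 one-sided and c = 1.960 two-sided.

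**(a) Success stops the trial; a non-significant interim continues.** Under no effect:

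- One-sided: 1 − P(Z1 ≤ c and Z2 ≤ c) = 1 − 0.9199 = 0.0801.
- Two-sided, only a significant reduction stops: false benefit 1 − 0.9584 = 0.0416, against 0.025 planned. Adding false harm at the final look (0.0250) gives a total of 0.0666.
- Two-sided, either direction stops: 1 − 0.9169 = 0.0831.

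A simulation of 4 million null trials gave 0.0802, 0.0417, 0.0667 and 0.0833 for these four quantities.

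**(b) The trial always ends at 100.** Type I error stays at 0.05. Under the design effect:

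| | One-sided | Two-sided |
|---|---|---|
| θ | 2.9264 | 3.2415 |
| Mean of Z1 = θ × 0.7071 | 2.0693 | 2.2921 |
| Power at 100 = Φ(mean − c) | Φ(0.424) = 0.664 | Φ(0.332) = 0.630 |
| Significant at both 100 and 200 | 0.6502 | 0.6185 |
| Significant at 200 but not at 100 | 0.90 − 0.6502 = 0.2498 | 0.90 − 0.6185 = 0.2815 |
| Not significant at 100 | 0.3356 | 0.3699 |
| Share of those significant at 200 | 0.2498 / 0.3356 = 0.744 | 0.2815 / 0.3699 = 0.761 |

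**(c) Non-significance stops; a significant interim continues to a final test.** Power is 0.65 one-sided or 0.62 two-sided, and type I error is 2.0% or 1.7%.

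**Sensitivity.**

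- With 40% of the information at the look, (a) becomes 8.3% one-sided. Two-sided it is 4.3% false benefit, 6.8% total and 8.6% either direction. Power in (b) falls to 0.58 or 0.54.
- If true fixed-design power is 0.80, power in (b) is 0.55 or 0.51; if 0.95, it is 0.75 or 0.72.

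**The case against.** The omission itself is not in dispute. The case against the figures has four parts.

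1. **The threshold is assumed.** The plan never equates success at the look with p<0.05, and stopping is discretionary. A strict unwritten threshold would inflate the error much less. This stands as a limit on the numbers: they illustrate the plain reading and are not fixed properties of the trial. It does not rescue the plan, since no strict threshold is written.
2. **Read literally, the final analysis is at 100 evaluable patients.** The two looks would then nearly coincide. At an assumed information fraction of 0.9, scenario (a) gives 6.3% one-sided or 3.2% false benefit two-sided, and the inflation vanishes as the fraction approaches 1. This also stands: 8.0% requires a final look at 200. But a trial sized for 0.90 at 200 and ended at 100 again has power of only about 0.66 or 0.63.
3. **The non-significance reason carries no time.** Only the success reason is tied to the first analysis. Placing the other at 100 patients is an inference, but only one interim is planned, and at the final analysis nothing is left to stop.
4. **Part of the remedy is choice.** O'Brien-Fleming, Pocock and a conditional-power rule are options. What is required is that a rule be written, or that the outcome look be dropped.

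**Conclusion.** The concern holds, and the plan must be changed before the look at 100 patients. Its stated stopping reasons do not guarantee both alpha 0.05 and power 0.90.

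The size depends on how the reasons are used. The success stop alone takes the false-benefit risk to 8.0% (one-sided) or 4.2% (two-sided). Deciding the trial at 100 keeps alpha but cuts power to 0.66 or 0.63. The power loss is the larger harm, because a trial could report no difference when it would probably have shown the effect it was sized for.

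These figures rest on a final number of 200, half the information at the look, unadjusted 0.05 at each look, and a true fixed-design power of 0.90, which cannot be checked without an SD.

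**What to change.** In Data Safety Monitoring and Reporting Plan:

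1. Reconcile the final analysis at 100 evaluable patients with 100 being the midpoint and with about 200 in Sample Size. The values below apply only if the final number is 200.
2. Delete the non-significance reason, or replace it with a non-binding futility threshold, for example conditional power below 20% under the design effect. With the O'Brien-Fleming boundary below, that fires only when liposomal bupivacaine is trending worse than control (interim z below −0.54 one-sided or −0.34 two-sided). That happens in about 0.5% or 0.4% of trials if the design effect is real.
3. Either make the midpoint review safety-only and remove the success reason, or define success for one named primary test on the in-hospital endpoint in the Hypothesis section, state whether alpha is one- or two-sided, and set a group-sequential boundary.

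| Boundary at half information | Interim p | Final p | Power at 200 |
|---|---|---|---|
| O'Brien-Fleming, one-sided | 0.0088 | 0.0467 | 0.896 |
| O'Brien-Fleming, two-sided | 0.0052 | 0.0480 | 0.898 |
| Pocock, one-sided | 0.0304 | 0.0304 | 0.870 |
| Pocock, two-sided | 0.0294 | 0.0294 | 0.870 |

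Recompute these if the information fraction is not one half. Under the boundary option the 7-10 day period becomes secondary or needs its own adjustment.

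**Cost.** A safety-only midpoint needs a few sentence edits and costs no power. O'Brien-Fleming costs under half a percentage point (power 0.896 or 0.897 if the futility rule is added and followed). The boundary option also requires edits to Statistical Analysis, and naming the primary test there is a real decision. No extra patients are needed if 200 is confirmed.
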